7.2.2. Treatment Exposure and Compliance

Population: SAF

Study drug exposure will be calculated for each subject as the total number of days on the treatment, from the date of the first wipe used to the date of the last wipe used. The number and percentage of subjects by treatment arm will be summarized according to the following duration-of-exposure categories: '1 - 7 days', '8 - 14 days', '15 - 21 days', '22 - 28 days' and ' ≥ 29 days'. In addition, these data will be summarized using descriptive statistics.

The number of missed days of dosing will also be determined as the number of days on study minus the total days of dosing, i.e., the (number of opened glass vials of wipes)/2. These results will be summarized using frequency distributions and descriptive statistics, as appropriate.

Dosing compliance will be computed as the proportion of doses taken over the dose-administration period (the time between the first dose of IP and the Day 29/EOS visit). The compliance percentage will be computed as the (number of opened glass vials of wipes)/2 divided by the number of days on study, times 100. These data will be provided as a listing giving the beginning and end dates for the dosing interval with the calculated compliance. The number and percentage of subjects by treatment arm will be summarized according to the following drug compliance categories: ' $\leq 50\%$ ', ' $> 50\% - 60\%$ ', ' $> 60\% - 70\%$ ', ' $> 70\% - 80\%$ ', ' $> 80\% - 90\%$ ', ' $> 90\% - 100\%$ ', and ' $> 100\%$ '. The overall compliance by treatment arm will be summarized using descriptive statistics.

7.2.3. Ocular Safety Assessments

Population: SAF

7.2.3.1. BCVA

BCVA will be measured at all visits and the Day 1 value will be used as the baseline value. The observed value and change from baseline will be summarized descriptively by visit and treatment arm for both eyes (SE and FE) in logarithm of the minimum angle of resolution (logMAR) units.

7.2.3.2. IOP

IOP (mmHg) will be measured at Screening, Baseline and Day 29 (Week 4). The observed values and changes from baseline will be summarized descriptively by visit and treatment arm for both eyes (SE and FE).

7.2.3.3. Slit Lamp Biomicroscopy

Slit lamp biomicroscopy will be performed at every visit during the study. The following anterior ocular structures will be evaluated at each exam:

- Lids (overall, erythema, edema)
- Conjunctiva (overall, hyperemia, edema)
- Cornea (overall)
- Anterior chamber (overall, cells, flare)
- Iris/Pupil (screening visit only)
- Lens (status, severity and opacity)

The number and percentage of subjects within each category will be summarized by visit and treatment arm for both eyes (SE and FE). Any open text field information will be presented in the data listings. In addition, shift tables will be prepared showing any categorical changes from baseline to each follow-up exam.

7.2.3.4. Dilated Ophthalmoscopy

A dilated ophthalmoscopy exam will be performed at Screening and Day 29 (Week 4), and the screening value will be used as the baseline value. Assessments on the following structures will be made during each exam:

- Vitreous
- Macula
- Retinal Vessels
- Peripheral Retina
- Optic Disc

The number and percentage of subjects within each category will be summarized by visit, treatment arm, and eye (SE and FE). In addition, shift tables will be prepared showing any categorical changes from baseline to the Week 4 exam.

7.2.3.5. VAS of IP Tolerability

A VAS evaluation of the IP tolerability will be performed at all visits and the Day 1 value will be used as the baseline value. Subjects will grade the tolerability of the IP after administration on a scale of 0 (no discomfort) to 100 (severe discomfort) by placing a vertical mark on the horizontal line shown below. The mark will be measured and recorded.

The VAS will be measured at all visits and the Day 1 value will be used as the baseline value. The observed value and change from baseline for each subsequent post-baseline visit will be summarized descriptively by visit and treatment arm.

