1.5 Risks and Benefits

Based upon previous human evaluation and this class of compounds, the primary potential risk of IVW-1001 is ocular discomfort. The potential benefits are improvements in signs and symptoms of ocular surface disease.

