6 ALLOCATION AND DOSING OF INVESTIGATIONAL PRODUCT

6.1 Allocation to Treatment Groups

After the vehicle run-in period, during which all subjects receive vehicle, qualified subjects will be randomized 1:1:1 to 1 of 3 treatment groups to receive one of the following: IVW-1001 Ophthalmic Eyelid Wipe 0.1%, IVW-1001 Ophthalmic Eyelid Wipe 0.2%, or vehicle.

6.1.1 *Subject Assignment*

All subjects will receive the same vehicle control run-in at the Screening Visit (single-masked), and at the Baseline Visit, subjects will receive and be dispensed IP according to the treatment group to which they are assigned.

6.1.2 *Study Eye Selection*

The study eye will be designated by Data Management at randomization at the Baseline Visit. If both eyes have an unanesthetized Schirmer's test score between 5 and 10 mm inclusive, the study eye will be the one with the lower score. If both eyes have the same an unanesthetized Schirmer's test score, the study eye will be the one with the highest qualifying total CFS score. However, if both eyes have the same total qualifying CFS score, the right eye will be designated as the study eye. Site personnel are not required to designate the study eye.

Note that dosing of study medication will be in both eyes (OU).

6.1.3 *Randomization Procedures*

Central randomization using the IWRS will be utilized to provide assignment of a specific anonymized code, corresponding to vehicle during the run-in period at the Screening Visit and separately to the IP to which the subject is randomized (IVW-1001 Ophthalmic Eyelid Wipe 0.1%, IVW-1001 Ophthalmic Eyelid Wipe 0.2%, or vehicle) at the Baseline Visit.

Trial treatment randomization codes and procedures for breaking codes will be maintained by the central randomization provider.

6.1.4 *Masking*

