7.5.2 Baseline/Randomization Visit (Day 1)

Procedures should be conducted in the following order:

- Eligibility determination
- Medical/Ophthalmic history
- Concomitant medications
- Collect run-in vehicle/compliance assessment
- Urine pregnancy test (WOCBP only)
- Eye Dryness Score VAS
- Ocular Discomfort Score VAS
- Investigational product ASHRAE 7-point comfort VAS (pre-dose)
- Best-corrected VA OU
- Slit lamp biomicroscopy OU
- Corneal fluorescein staining OU
- First unanesthetized Schirmer's test OU (≥ 15 minutes post-CFS)
- Anesthetized Schirmer's test OU
- Intraocular pressure OU

- Randomization
- In-office IP administration OU (≥ 20 minutes post-CFS)
- Investigational product ASHRAE 7-point comfort VAS (5 ± 2 minutes post-dose)
- Symptom Assessment in Dry Eye questionnaire ($5 + 10$ minutes post-dose)
- Investigational product tolerability VAS ($5 + 10$ minutes post-dose)
- Investigational product ASHRAE 7-point comfort VAS (15 ± 2 minutes post-dose)
- Second unanesthetized Schirmer's test OU ($\geq 20 \pm 5$ minutes post-dose)Investigational product ASHRAE 7-point comfort VAS (30 ± 5 and 60 ± 5 minutes post-dose)
- Anesthetized Schirmer's test OU (post final Investigational Product ASHRAE 7-point comfort VAS)
- Dispense IP
- Adverse event assessment

7.5.3 Visit 3 (Day 8 ± 1 day), Visit 4 (Day 15 ± 2 days), and Visit 5 (Day 22 ± 2 days)

Procedures should be conducted in the following order:

- Concomitant medications
- Collect IP/compliance assessment/dispense IP
- Eye Dryness Score VAS
- Ocular Discomfort Score VAS
- Investigational product ASHRAE 7-point comfort VAS (pre-dose)
- Best-corrected VA OU
- Slit lamp biomicroscopy OU
- Corneal fluorescein staining OU
- Unanesthetized Schirmer's test OU (≥ 15 minutes post-CFS)
- In-office IP administration OU (≥ 20 minutes post-CFS)
- Investigational product ASHRAE 7-point comfort VAS (5 ± 2 minutes post-dose)
- Symptom Assessment in Dry Eye questionnaire ($5 + 10$ minutes post-dose)
- Investigational product tolerability VAS ($5 + 10$ minutes post-dose)
- Investigational product ASHRAE 7-point comfort VAS (15 ± 2 minutes post-dose)

- Investigational product ASHRAE 7-point comfort VAS (30 ±5 and 60 ±5 minutes post-dose)
- Adverse event assessment

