- [e] Refraction at Visit 1 only unless ≥ 3 line reduction in VA.
- [f] Unanesthetized Schirmer's to be performed at least 15 minutes post-CFS.
- [g] Unanesthetized Schirmer's to be performed 20 ± 5 minutes post-IP administration.
- [h] Anesthetized Schirmer's to be performed after unanesthetized Schirmer's.
- [i] Anesthetized Schirmer's to be performed post final IP ASHRAE 7-point comfort VAS.
- [j] IOP to be performed post anesthetized Schirmer's.
- [k] Assignment of run-in IP (vehicle).
- [l] IP administration must be performed at least 20 minutes after completion of CFS. Subjects should not dose IP at home the morning of Visits 2, 3, 4, 5, or 6.
- [m] SAnDE questionnaire and IP tolerability VAS to be performed between 5 and 15 minutes post-dose.

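### The Day 1 tolerability VAS in SAP 7.2.3.5 is labelled baseline but is rated after the first randomised dose, so its change score shows drift on treatment rather than discomfort caused by the product

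*SAP*

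**What the plan says.** SAP 7.2.3.5 states twice that Day 1 supplies the baseline for IP tolerability; the first statement is that the VAS is "performed at all visits and the Day 1 value will be used as the baseline value". The same section describes a rating given after the product is applied, from 0 (no discomfort) to 100 (severe). It then plans the output: "The observed value and change from baseline for each subsequent post-baseline visit will be summarized descriptively by visit and treatment arm".

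The timing is set elsewhere. SAP 2.3, Table 1, footnote m reads: "SAnDE questionnaire and IP tolerability VAS to be performed between 5 and 15 minutes post-dose". Protocol 7.5.2 gives a fixed order for the Baseline Visit, in which the item "Investigational product tolerability VAS" comes after randomisation and after in-office dosing. On which product is used, Protocol 6.1.1 says that "at the Baseline Visit, subjects will receive and be dispensed IP according to the treatment group to which they are assigned".

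The measure matters to this trial. Protocol 1.5 says that "the primary potential risk of IVW-1001 is ocular discomfort", and Protocol 2.2.1 lists the tolerability VAS among the primary safety measures. Protocol 9.5 plans both absolute values and changes from baseline for the tolerability assessment.

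**The concern.** A baseline is useful in a safety table because it precedes the exposure under study. Most Visit 2 examinations meet that test: acuity, slit lamp, staining, the first unanesthetised Schirmer's test and IOP all come before randomisation in Protocol 7.5.2. The tolerability VAS does not. Its Day 1 value already contains any discomfort the assigned wipe causes, and subtracting it from later values removes that first-dose effect from the change column.

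Two consequences follow. First, someone who compares change columns across arms to judge tolerability could see no difference, or one favouring active, while active is still the less comfortable product. Second, the planned-output sentence refers to visits after baseline, and SAP 6.3 does not include tolerability in its list of Day 1 variables. Read literally, no defined by-arm table has to show the first-dose rating. That is the reading on first contact with the drug, taken before anyone can withdraw from the treatment period.

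**Working it through.** The documents give no expected value, SD or power for the tolerability VAS, so there is no plan figure to reproduce. The check has three parts.

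**1. Order of events at Visit 2** (Protocol 7.5.2 and 6.1.1; SAP Table 1, footnote m)

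Randomisation → in-office dose of the assigned product → tolerability VAS 5 to 15 minutes post-dose. Day 1 is also the date of initial treatment administration in SAP 2.2. The Day 1 value is therefore the first on-treatment rating. The only tolerability rating before randomisation is at Screening, after the run-in vehicle wipe (Protocol 7.5.1).

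**2. What the change score measures**

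Let d be the active-minus-vehicle difference in mean VAS on Day 1, and k the fraction of it present at a later visit.

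- Observed difference at the later visit: kd
- Difference between the arms' mean changes from Day 1: kd − d = (k − 1)d

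This is an identity. It needs no SD or sample size, and it says nothing about how large d or k will be. The table uses assumed d of 5, 10 and 20 points; positive values mean active is worse.

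| k | Observed difference, kd (d = 5 / 10 / 20) | Difference in change, (k − 1)d (d = 5 / 10 / 20) |
|---|---|---|
| 1.25 | +6.25 / +12.5 / +25 | +1.25 / +2.5 / +5 |
| 1 | +5 / +10 / +20 | 0 / 0 / 0 |
| 0.75 | +3.75 / +7.5 / +15 | −1.25 / −2.5 / −5 |
| 0.5 | +2.5 / +5 / +10 | −2.5 / −5 / −10 |
| 0.25 | +1.25 / +2.5 / +5 | −3.75 / −7.5 / −15 |
| 0 | 0 / 0 / 0 | −5 / −10 / −20 |

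For 0 < k < 1 the two columns have opposite signs. At k = 1 the change difference is zero whatever the size of d. At k = 0 there is no remaining excess, so the change shows a fall but contradicts nothing in the observed column.

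The same result at arm level, with assumed profiles and vehicle constant at 5:

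- Active constant at 30: change 30 − 30 = 0, the same as vehicle (5 − 5 = 0); observed gap 30 − 5 = +25.
- Active falling from 40 to 20: change 20 − 40 = −20 against 0 for vehicle; observed gap at Week 4 is 20 − 5 = +15.

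**3. Whether Day 1 appears by arm**

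The SAP 7.2.3.5 sentence ties its summaries to post-baseline visits. SAP 6.3 names IP comfort, EDS, ODS and SAnDE as Day 1 variables, but not tolerability. SAP 7.2 plans absolute values for continuous safety variables without naming visits. Nothing excludes Day 1, but nothing specifically requires it.

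**The case against.** The strongest reply is that the right summary is already planned. SAP 7.2.3.5 asks for the observed value in the same sentence as the change, and Protocol 9.5 and SAP 7.2 plan absolute values. Protocol 2.2.1 and SAP 7.2 list tolerability as its own item, outside the change-from-baseline measures. All data are listed, and adverse events are collected from the first IP dose (Protocol 8.5). A constant 30 against 5 would be plain in the observed column at every later visit. No between-arm difference, test or decision rule is attached to tolerability, so (k − 1)d is something a reader would compute, not an output the SAP promises. All of this stands, and it limits the harm.

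The reply on Day 1 stands in part. The phrase about later visits may qualify only the change, and near-identical sentences in SAP 7.4.1.1, 7.4.1.2 and 7.4.1.4 suggest template wording. The omission is therefore one possible reading, not a stated exclusion.

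A reader might infer more than the documents support:

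- *That the change score gives the wrong sign whenever discomfort fades.* Within an arm, a negative change is correct, because discomfort did fall. The misleading sign arises only when changes are compared across arms as a measure of tolerability.
- *That the design pushes the change score in active's favour.* The protocol says only this of the run-in: "After the vehicle run-in period, during which all subjects receive vehicle". Neither document describes adaptation to the wipe or to the drug. The direction depends on k, and at k = 1.25 the change is still against active.
- *That the discomfort signal is lost.* It is not, for the reasons above.

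**Conclusion.** Wrong as written, low severity. The documents alone establish that the value called baseline is rated after the first randomised dose. It follows by identity that the arms' changes differ by (k − 1)d. The point sizes in the table rest on assumed d and k and are illustrations only. What needs correcting is a mislabelled change column on the protocol's named main risk, together with wording that leaves it unclear whether the first-dose rating is tabulated by arm. No hypothesis, power figure or visit procedure is affected.

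**What to change.** In SAP 7.2.3.5:

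1. Remove both statements that the Day 1 value is the baseline.
2. Summarise the observed post-dose tolerability VAS by arm at Day 1 (named as the first randomised dose) and at Weeks 1, 2, 3 and 4.
3. Rename any change score *change from first randomised dose*, or drop it. If it is dropped, add an entry to SAP 7.7, because Protocol 9.5 names changes from baseline for this assessment. Renaming keeps the calculation.
4. Treat any change from the Screening vehicle rating as supportive.

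An assessment-specific reference has a precedent in the SAP: section 7.2.3.4 takes the screening value as baseline for ophthalmoscopy. The cost is minor SAP wording and table programming, with no new data and no change to visits. Dropping the change score would lose a simple display of drift, but the observed values by visit still show it.

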7.2.4. Non-Ocular Safety Assessments

Additional non-ocular safety assessments will be presented as follows:

- Urine Pregnancy Test (listing only)

7.3. Primary Efficacy Endpoint and Estimand

7.3.1. Primary Efficacy Endpoint and Considerations

The primary efficacy endpoint of the study is defined as:

- The mean change from baseline at Day 29 (Week 4/EOS) in the study eye of the unanesthetized Schirmer's test in the mITT population.

7.3.1.1. Unanesthetized Schirmer's Test

The unanesthetized Schirmer's test will be performed at least 15 minutes after CFS at each visit in each eye. In brief, a standardized Schirmer's test strip will be placed towards the temporal third of the lower eyelid of both eyes. The subject is left in a darkened room for 5 minutes, and the strips are then removed. The amount of wetting for each eye is recorded in mm by comparison to a ruler. The value recorded at Visit 2 will be used as the baseline value.

For the exploratory efficacy analysis, an evaluation of the proportion of subjects with a ≥ 10 mm increase in the unanesthetized Schirmer's test score at Day 29 (Week 4) will be summarized by the frequency and percentage of subjects in each category. Categorical comparisons will be evaluated using the methodology outlined in Section 7.4.3.

7.3.2. Primary Efficacy Estimand

The primary estimand includes the 4 attributes as described in the International Council for Harmonisation (ICH) E9 (R1) addendum on estimands and sensitivity analysis in clinical trials (population of interest, endpoint of interest, specification of how intercurrent events are reflected, and population-level summary), and is described for this study as follows:

Primary Estimand: The difference between IVW-1001 and Vehicle in the mean change from baseline at Day 29 (Week 4) in the study eye in the unanesthetized Schirmer's test score estimated using all data collected from the mITT population.

7.3.3. Primary Efficacy Analytical Approach

For the analysis of the primary efficacy endpoint (mean change from baseline at Week 4/EOS in the study eye of the unanesthetized Schirmer's test in the mITT population), the mean changes from baseline will be analyzed using a mixed model for repeated measures (MMRM), with a restricted maximum likelihood approach for model fitting. This MMRM model will include the fixed effects of Treatment (IVW-1001 Ophthalmic Wipe 0.2%, IVW-1001 Ophthalmic Wipe 0.2%, or Vehicle), Visit, and Treatment*Visit interaction, with the baseline value of the outcome parameter included as a covariate, and with Subject included as a subject effect. Additional baseline and other covariate parameters will be assessed for possible inclusion into the model. An unstructured correlation structure will be used to model the within-subject errors. If there is a failure of the model to converge, then variance components (vc), first-order autoregressive [ar(1)], and compound symmetry (cs) correlation structures will be tested. The correlation structure indicating the best fit based on Akaike's Information Criterion (AIC) will be used for the analysis. Significance assessments will be 2-sided and based on least-squares means with a significance of 0.05 for each endpoint. The results from the model will describe the least-squares adjusted mean differences from baseline with standard errors and their associated confidence intervals.

Sample code for the change from baseline outcome parameter will be analyzed using SAS as follows (please note that the code is approximate and may be adjusted as needed at the discretion of the statistician upon review of the data structure and model convergence):

```
proc mixed data=IVIEW_Data;
  class Visit Treatment SubjectID;
  model Parameter_CFB = Parameter_Baseline Treatment Visit
  Treatment*Visit / solution;
  repeated Visit / type=un subject=SubjectID;
  lsmeans Visit*Treatment / pdiff cl alpha=0.05;
  estimate "X Dose vs. Vehicle Comparison" Visit*Treatment
  1 -1/ cl;

run;
quit;
```

The variables in the model statement are defined as follows:

- Parameter_CFB: The dependent variable representing the mean CFB of the outcome variable in question
- Parameter_Baseline: The value of the outcome variable at baseline
- Treatment: The treatment group designated at baseline
- Visit: The study visit timepoint
- Treatment*Visit: The interaction between treatment group and visit

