3. HYPOTHESIS, SAMPLE SIZE AND POWER

3.1. Statistical Hypothesis

The primary efficacy endpoint is the mean change from baseline (CFB) at Day 29 (Week 4/EOS) in the SE in the unanesthetized Schirmer's test.

The clinical hypothesis is that IVW-1001 Ophthalmic Eyelid Wipe administered BID bilaterally for 29 days is more effective than Vehicle when evaluating tear production in subjects with DED.

The following 2-sided hypothesis will be tested:

$$H_0: \Delta = 0$$

$$H_a: \Delta \neq 0$$

Where Δ is the difference in mean CFB in the unanesthetized Schirmer's score as measured at Day 29 (Week 4) between the IVW-1001 Ophthalmic Eyelid Wipe and Vehicle treated groups.

In brief, the null hypothesis indicates that the mean CFB in the unanesthetized Schirmer's score as measured at Day 29 for subjects treated with IVW-1001 Ophthalmic Eyelid Wipe 0.2% or IVW-1001 Ophthalmic Eyelid Wipe 0.1% will not differ from the mean CFB in the unanesthetized Schirmer's score for subjects treated with Vehicle. The alternative hypothesis indicates that there is a significant difference at Day 29 between subjects treated with IVW-1001 Ophthalmic Eyelid Wipe and subjects treated with Vehicle.

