3.3. Multiplicity Adjustment

Due to the early phase of the study and because the primary objective is the assessment of safety, there will be no adjustments for multiplicity in the testing of the efficacy endpoints.

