Treatment-group comparisons will include IVW-1001 Ophthalmic Wipe 0.2% vs. Vehicle and IVW-1001 Ophthalmic Wipe 0.1% vs. Vehicle for the primary and exploratory efficacy endpoints. Statistical tests will be presented as two-sided p-values rounded to four decimal places; p-values less than 0.0001 will be presented as '<0.0001' and p-values = 1 will be presented as '>0.999' in all tables. Efficacy analyses will be carried out using a two-sided, $\alpha = 0.05$ significance level without adjustments for multiplicity, as this is a Phase 1/2a study.

All data collected in this study will be presented in individual data listings for all subjects.

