7.7. Changes to Protocol-Planned Analyses

Changes to the protocol-planned analyses include the following:

- The protocol indicates that as a sensitivity analysis, the primary and secondary efficacy endpoints will be analyzed using the PP population. The secondary endpoints were meant to be defined as 'exploratory' as no efficacy endpoints are defined in the protocol as secondary. Since the primary objective of the study is safety and all the exploratory endpoints will be analyzed at all visits using the mITT population, only the primary endpoint will be analyzed using the PP population.
- The protocol indicates that for the efficacy endpoints, missing data will be imputed using last observation carried forward. Since the amount of missing efficacy data throughout the study is very small, no imputation for missing data will be performed.
- The protocol indicates that for the efficacy endpoints, appropriate methods will be used to control the Type I error rate for multiple comparisons of the 2 dose groups versus the control. Since this is an early phase study where the primary objective is safety, and because there are many endpoints being tested at all visits (primary and exploratory), no multiplicity adjustments will be performed.

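### Does the SAP define a single IVW-1001-versus-vehicle comparison while planning two unadjusted dose tests?

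*SAP*

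**What the plan says.** The wording that raises the question:

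- SAP 3.1 defines one Δ, the difference in mean Day 29 change "between the IVW-1001 Ophthalmic Eyelid Wipe and Vehicle treated groups". The explanatory paragraph after it names both the 0.2% and the 0.1% wipe.
- SAP 2.1 and 7.3.2 give the primary estimand as "The difference between IVW-1001 and Vehicle in the mean change from baseline at Day 29 (Week 4) in the study eye", with no dose named.
- SAP 7.3.3 specifies a mixed model with "fixed effects of Treatment (IVW-1001 Ophthalmic Wipe 0.2%, IVW-1001 Ophthalmic Wipe 0.2%, or Vehicle" and continues: "Significance assessments will be 2-sided and based on least-squares means with a significance of 0.05 for each endpoint". Its sample code requests differences among all visit-by-treatment means and includes an estimate line labelled for a generic dose against vehicle.

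The wording that answers it:

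- SAP 7.1 lists two comparisons, 0.2% against vehicle and 0.1% against vehicle, for the primary and the exploratory endpoints, at a two-sided 0.05 "significance level without adjustments for multiplicity, as this is a Phase 1/2a study".
- SAP 3.2 states power for each dose group against vehicle.
- SAP 3.3 says "there will be no adjustments for multiplicity in the testing of the efficacy endpoints". SAP 7.7 records this as a departure from the protocol: "there are many endpoints being tested at all visits (primary and exploratory), no multiplicity adjustments will be performed".

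On sample size, Protocol 9.2 uses 3.3 mm at two-sided 0.025, and SAP 3.2 uses 3.0 mm at two-sided 0.05. Both assume 46 completers per group and an SD of 5.0 mm. SAP 7.7 does not list this difference. The SAP's version history ties it to the protocol of 17 April 2024, while its reference list cites Version 1.0 of 22 January 2024.

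**The concern.** Hypothesis and estimand text tends to be carried into the study report. Here it describes a single difference for a drug given at two doses, and the model section names only one of them. Setting 0.05 per endpoint leaves open whether the two doses share that 0.05 or each receive it.

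The readings would differ in substance. A test pooling the two active arms against vehicle has good power if both doses work and poor power if only one does. Two separate unadjusted tests keep power per dose but give two chances of a false positive on the primary endpoint, and the SAP does not state that joint rate.

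The list of changes in SAP 7.7 also looks incomplete. It drops the Type I error control but does not say that the power calculation moved with it. The same section observes: "Since the amount of missing efficacy data throughout the study is very small". That suggests it was written with some study data in view, when a complete list of changes matters more.

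**Working it through.** **Inputs.** n = 46 completers per group and SD 5.0 mm (Protocol 9.2, SAP 3.2); 1:1:1 allocation with a shared vehicle arm (SAP 2.2); 3.3 mm at 0.025 (Protocol 9.2); 3.0 mm at 0.05 (SAP 3.2).

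**1. The documents' own power figures.** The standard error of a dose-minus-vehicle difference is 5.0 × √(2/46) = 1.043 mm. The standardised effect is 3.0/1.043 = 2.878 or 3.3/1.043 = 3.165. Normal-approximation power is Φ(effect − z), with z = 1.960 at 0.05 and 2.241 at 0.025. The last column uses the noncentral t with 90 df.

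| Difference | Two-sided α | Normal | Noncentral t |
|---|---|---|---|
| 3.3 mm | 0.025 (protocol) | 82.2% | 81.0% |
| 3.0 mm | 0.05 (SAP) | 82.1% | 81.2% |
| 3.0 mm | 0.025 | 73.8% | 72.4% |
| 3.3 mm | 0.05 | 88.6% | 87.9% |

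Both claims of at least 80% power hold. Enrolment also reproduces: 46/(1 − 0.08) = 50 per group.

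**2. Where the move from 3.3 to 3.0 mm comes from.** With n and SD fixed, the smallest difference detectable with 80% power (t) is 3.26 mm at 0.025 and 2.95 mm at 0.05. Rounded up to one decimal, these are 3.3 and 3.0 mm. The new power basis is the old one recomputed at the unadjusted level.

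**3. Joint false-positive rate, neither dose working.** The two differences share the vehicle mean, so their covariance is σ²/n and each variance is 2σ²/n. The correlation is therefore 0.5. The chance of at least one p<0.05 is 1 − P(|Z₁|<1.96 and |Z₂|<1.96) = 9.07%. Simulated t tests with a common variance estimate (135 df) give 9.04%, of which the favourable direction accounts for 4.5%. Independent tests would give 1 − 0.95² = 9.75%. At 0.025 per dose the joint rate is 4.65%.

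**4. What a pooled reading would mean.** The standard error for 92 against 46 is 5.0 × √(1/92 + 1/46) = 0.903 mm. If both doses have 3.0 mm, power is 91.0%. If only one does, the pooled difference is 1.5 mm and power is 37.8%, against 81.5% for that dose's own test (135 df).

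**5. Which reading the text supports.** SAP 7.1, SAP 3.2, the explanation in SAP 3.1, the two-dose wording in SAP 7.7 and the generic-dose estimate line in SAP 7.3.3 all point to two comparisons. Neither document proposes pooling, and the model has no pooled level. A three-level treatment list with 0.2% printed twice can only be 0.2%, 0.1% and vehicle. SAP 7.4 sends the other change-from-baseline endpoints to SAP 7.3.3, so stating 0.05 per endpoint there is natural, and SAP 7.1 supplies the per-dose rule.

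**The case for a change.** The best case for editing is that it costs nothing and the mismatches are real. The Δ and the estimand name no dose, the exploratory estimands in SAP 7.4.2 repeat the same wording, and SAP 7.3.3 has a plain error in its treatment list. SAP 1 says the SAP's methods supersede the protocol's, so its defining sections ought to be exact. At 46 per group, 3.0 mm has only 72.4% power at the protocol's 0.025, so the SAP's power claim depends on the larger α, and SAP 7.7 does not say so.

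All of that stands as description. None of it alters a test, an estimate or the sample size. The larger α follows from dropping multiplicity control, which SAP 7.7 does list, and SAP 3.2 prints the new basis in full. The 22 January 2024 entry is a stale citation: the version history identifies the governing protocol, whose synopsis and section 9.2 agree on 3.3 mm at 0.025. The remark about missing data shows at most knowledge of missingness, which can be had while masked, and says nothing about how the comparisons are defined.

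Calling the p-values nominal and printing the 9% would be good practice. A reader who knows that two tests at 0.05 share a control arm and are unadjusted already has what is needed to interpret them.

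**Conclusion.** No change is called for. The unnamed dose is a gap that SAP 7.1 and 3.2 fill without ambiguity. The repeated 0.2% and the stale protocol citation are clerical slips. The unadjusted testing is a disclosed trade-off: about 81% power per dose at 3.0 mm, in exchange for a joint false-positive rate of about 9% (about 4.5% favourable) on the primary endpoint. That is reasonable where safety is the primary objective and efficacy is being explored. The pooled analysis that would make the wording consequential is not planned.

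The figures assume equal group sizes, a common SD of 5.0 mm and simple two- or three-group comparisons; the baseline-adjusted repeated-measures model may differ somewhat. The 9% covers only the two primary dose tests with neither dose working, not the exploratory endpoints or other visits.
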